1.1. Study summary

Design

The COMET-19 study is a prospective cohort study that aims to compare the prevalence of coronary microvascular dysfunction (CMD) in patients with stable angina who have a history of severe COVID-19 infection and those with stable angina without a history of COVID-19.

Aims

The primary aim of the study is to determine whether a history of severe COVID-19 infection impacts the prevalence of CMD and its endotypes in stable angina patients.

Outcome measures

The primary outcome measure will be the prevalence of CMD in both groups, measured by both coronary flow reserve (CFR) and index of microvascular resistance (IMR) using a pressure-temperature wire.

Population

The study population for the COMET-19 trial consists of adult patients (aged 40 -80 years) with a clinical diagnosis of stable angina. They will be recruited from two university hospitals in Lithuania: Seamen's Branch, Klaipeda University Hospital, Klaipeda, and the Hospital of Lithuanian University of Health Sciences Kaunas Clinics, Kaunas.

Eligibility

Eligible patients will be those who have been diagnosed with stable angina and are scheduled to undergo angiography and possible revascularization. The study population will be divided into two groups:

Group A: Patients with stable angina and a history of severe COVID-19 infection.

Group B: Patients with stable angina without a history of COVID-19 infection. This group serves as a comparison group to assess the potential differences in CMD prevalence.

Duration

Anticipated recruitment is 6 months. Follow-up will occur 3 months after coronary angiography

1.2. Glossary of abbreviations

CAD	Coronary artery disease
CVD	Cardiovascular disease
CMD	Coronary Microvascular Dysfunction
IMR	Index of Microvascular Resistance
PCI	Percutaneous Coronary Intervention
SAQ	Seattle Angina Questionnaire
IVUS	Intravascular ultrasound

2. Introduction

2.1. Background

Cardiac involvement has been well-documented during the acute phase of SARS-CoV-2 infection, with some patients experiencing persistent symptoms even after recovery, referred to as long-COVID-19 syndrome(1). A subset of these patients may develop angina-like chest pain, which remains a poorly understood phenomenon(2).

In recent years, there has been growing attention towards the assessment of microvascular function in patients with coronary artery disease, as it has been shown to be a predictor of adverse clinical outcomes, including persistent angina (3). The invasive measurement of the index of microcirculatory resistance (IMR) along with coronary flow reserve (CFR) has been established as a reliable tool for evaluating microvascular function in this context(3).

However, the mechanisms underlying persistent chest pain and potential microvascular dysfunction in patients with long-COVID-19 syndrome have not been adequately explored. To address this gap in knowledge, the preset study aims to compare the prevalence of CMD in patients with stable angina and a history of severe COVID-19 infection requiring oxygen supplementation, with those without a history of COVID-19. The study will employ a prospective design, utilizing a pressure-temperature wire to assess CMD in both groups of patients.

The findings from this study have the potential to contribute to a better understanding of the underlying mechanisms of persistent chest pain in patients with long-COVID-19 syndrome and may have implications for the management of this patient population.

3. Study objectives

3.1 Primary, Secondary and Tertiary Objectives

1. Primary objectives:

To determine if there is a significant difference in the prevalence of coronary microvascular dysfunction (CMD) between patients with stable angina who have had a severe COVID-19 infection (Group A) and those stable angina without a history of COVID-19 (Group B). This will be measured using both coronary flow reserve (CFR) and index of microvascular resistance (IMR) through the pressure-temperature wire.

2. Secondary Objectives:

- I. To assess the severity of CMD, as indicated by the CFR and IMR values, in both groups. This will allow for a deeper understanding of the extent of CMD in each group.
- II. To evaluate any potential correlation between the duration of oxygen supplementation (in days) in the COVID-19 group and the incidence and severity of CMD. This could provide insight into whether the length of severe illness contributes to the risk or extent of CMD.
- III. To investigate which CMD endotype (structural or functional) predominates in both groups.

3. Tertiary Objectives:

- I. To investigate the patient-reported outcomes in both groups, especially in relation to symptoms of angina, quality of life, and functional status. This would give insight into how CMD affects patients' day-to-day lives and well-being.

3.2 Rationale for the study

The aftermath of the COVID-19 pandemic has unveiled a plethora of lingering health complications in those who have recovered, notably the 'long-COVID' or 'post-acute sequelae of SARS-CoV-2 infection' (PASC). Among these post-recovery symptoms, cardiovascular complications, especially angina-like chest pain, have surfaced as a significant area of concern. The possible mechanisms range from direct viral injury to the heart, systemic inflammatory responses, microvascular damage, to increased thrombotic events. Given this backdrop, understanding the potential link between severe COVID-19 infection and coronary microvascular dysfunction (CMD) becomes crucial, especially since CMD is known to predict adverse outcomes, such as persistent angina and heart failure, in other contexts.

Established diagnostic methods, such as the IMR and CFR measurements via a pressure-temperature wire, offer a reliable avenue to investigate this microvascular function. Currently, there is a knowledge gap regarding the long-term cardiovascular implications of COVID-19, specifically in relation to CMD. By investigating the incidence of CMD in those with a history of severe COVID-19 against those without, the study aims to ascertain whether the virus plays a direct role in the onset of CMD, providing clarity in an area currently clouded with uncertainties.

In essence, the COMET-19 study seeks to bridge the existing knowledge chasm concerning cardiovascular consequences in post-COVID-19 patients. The findings will not only provide insights into the causative relationship between COVID-19 and CMD but will also guide clinical decisions, and patient management, ultimately improving outcomes for those recovering from severe forms of the virus.

3.3 Study hypotheses

 Primary Hypothesis:

- i. Patients with a history of severe COVID-19 infection (those who required oxygen supplementation) (Group A) will have a higher prevalence of CMD (IMR > 25 or CFR < 2.0) than patients without a history of COVID-19 infection (Group B).

 Secondary Hypotheses:

[figure not shown]
- i. Patients in Group A will have more severe CMD than patients in Group B.
- ii. The severity of CMD will correlate with the duration of oxygen supplementation.

 Tertiary Hypothesis:

- i. Group A will have worse patient-reported health outcomes than patients in Group B.

13. Study design

4.1 Study overview diagram

4.2 Study protocol:

Following enrollment in the study patients should undergo the following:

Baseline assessment:

- A. Demographics:
 - Age
 - Gender
 - Center
 - Rural vs Urban
- B. Medical History:
 - History of cardiovascular diseases (specifically any known coronary artery disease)
 - History of diabetes, hypertension, or other comorbid conditions
 - Medications currently being taken
 - Past surgeries or medical interventions
- C. COVID-19 Specific History (for Group A):
 - - Date of COVID-19 diagnosis
 - - Duration of hospitalization
 - - Length of time on oxygen supplementation
 - - Any other COVID-19 related complications experienced
- D. Clinical Assessment:
 - Vital signs (Blood Pressure, Heart Rate, Respiratory Rate, Temperature, Oxygen Saturation)
 - - Body Mass Index (BMI)
 - -Physical examination focusing on the cardiovascular system
- E. Symptom Assessment:
 - Onset, frequency, duration, and severity of angina symptoms
 - Presence of any other cardiovascular symptoms (e.g., shortness of breath, palpitations)
 - New York Heart Association classification
- F. Diagnostic Tests:
 - Electrocardiogram
 - Echocardiogram or other imaging if available and relevant
 - Blood tests (cardiac markers, lipid profile, Inflammatory markers, blood glucose, blood counts and renal function panel)
- G. Patient-Reported Outcomes:
 - Quality of Life assessment, (Seattle angina score)

H. Risk Factors:

-  - Smoking history
-  - Alcohol consumption
-  - Physical activity levels
-  - Family history of cardiovascular diseases

I. Review of Previous Treatments (if any):

-  - Medications previously prescribed for angina (Trimetazidine, Ranolazine, cardiovascular related drugs)

Functional assessment

Functional assessment will be performed just after undergoing the diagnostic coronary angiography

Invasive functional assessment

- Upon intubation of the guiding catheter, 300 mcg of intra-coronary glyceryl-trinitrate will be administered to control coronary vasomotor tone.
- Coronary flow reserve (CFR), fractional flow reserve (FFR), and index of microvascular resistance (IMR) will be assessed using the CoroFlow system (Coroventis Research AB, Uppsala, Sweden).

4.3. Study outcome measures

Primary Outcome:

- Prevalence of coronary microvascular dysfunction (CMD)

Secondary Outcomes:

- Severity of CMD
- Correlation of the severity of CMD and the duration of oxygen supplementation (days) in group A.
- Prevalence of CMD endotypes in both groups
- Seattle Angina Questionnaire score.

4.4. Relevance and Implications of the Trial Results

- Clarity in Cardiovascular Consequences: With COVID-19 known to affect multiple organ systems, including the cardiovascular system, understanding the potential long-term implications becomes paramount. Determining whether there's a direct link between severe COVID-19 infection and CMD will shed light on this critical area of uncertainty.
- Guidance for Clinical Decisions: If a significant association between severe COVID-19 and CMD is established, this could directly impact clinical decisions. It may necessitate a different approach or more frequent monitoring for COVID-19 survivors presenting with angina-like symptoms.
- Informed Patient Management: For patients who have recovered from severe COVID-19 infections, knowing the potential risks and understanding the importance of regular cardiac check-ups will be pivotal. An informed patient is better equipped to participate actively in their care and adhere to medical advice.
- Potential for Further Research: The results of this trial could set the stage for additional studies, especially focused on therapeutic interventions, management strategies, and possibly preventive measures for at-risk populations.

4.5. Sample size/Power calculation

Prior literature suggests that the prevalence of CMD in patient with stable angina is approximately 10% (4). There is minimal data on the prevalence of CMD in stable angina patients with a history of COVID-19 infection. Limited preliminary data from the ANGI-Covid study suggests the prevalence to be approximately 50% (5).

After adjusting each estimated prevalence 5% towards each other, the estimated prevalence of CMD in patients with stable angina was set at 15% and in patients with stable angina with a history of COVID-19 infection at 45%. For a study power of 0.9, we will require a total of 94 patients in the study, with 47 patients in each arm of the study. Given the uncertainty regarding the estimated prevalence of CMD in patients with stable angina with a history of COVID-19 infection, this study will adopt an adaptive study design. Once enrollment has been completed based on the abovementioned estimates, the necessary sample size will be re-assessed to statistical power based on the observed prevalence of CMD within in each of the present cohort. At that time, the decision will be made to continue or halt enrollment depending on whether the necessary number of enrollees for statistical significance for the primary endpoint has been reached.

13. Participant entry

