5.3. Exclusion criteria

1. Acute coronary syndromes (unstable angina, non-ST elevation myocardial infarction, or ST-elevation myocardial infarction).
2. History of myocardial infarction.
3. Ejection Fraction ≤ 40%
4. Obstructive coronary artery disease
5. History of coronary artery bypass graft surgery.
6. Severe kidney disease (eGFR <30 mL/min/1.73 m²).
7. Severe liver disease or liver function test abnormalities (aspartate aminotransferase or alanine aminotransferase levels >3 times the upper limit of normal).
8. Patients who are allergic to adenosine (since hyperemia during IMR measurement is achieved by adenosine injection).
9. Significant valvular heart disease or cardiomyopathy.
10. Patients who are pregnant or breastfeeding.
11. Patients on chronic supplemental oxygen therapy prior to their diagnosis of COVID-19 infection
12. Patients who are unable to comply with study requirements.

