9.1. Ethics approval

This study will involve human subjects and as such, ethical considerations will be paramount. The study will be conducted in accordance with the principles of the Declaration of Helsinki and will comply with all relevant laws and regulations. All patients will be fully informed of the risks and benefits of participation in the study and will provide written informed consent prior to enrolment. The Chief Investigator will obtain approval from the Kaunas regional biomedical research ethics committee.

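### Does the target of 94 patients fall short of 0.9 power because some enrolled patients will prove ineligible or unmeasured at angiography?

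*Combined protocol and SAP*

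**What the plan says.** Section 4.5 (Sample size/Power calculation) takes CMD prevalences of about 10% in stable angina and 50% after COVID-19 from prior literature and limited preliminary data. It moves each 5 points towards the other, to 15% and 45%, and concludes: "For a study power of 0.9, we will require a total of 94 patients in the study, with 47 patients in each arm". It then plans a re-assessment, which starts "Once enrollment has been completed based on the abovementioned estimates" and uses the prevalence observed in each cohort. Enrolment continues or halts "depending on whether the necessary number of enrollees for statistical significance for the primary endpoint has been reached".

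On the order of events:

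- Section 1.1 (Eligibility) describes patients who "are scheduled to undergo angiography and possible revascularization".
- Section 9.1 says that patients "will provide written informed consent prior to enrolment".
- Section 4.2 lists the study procedures under the lead-in "Following enrollment in the study patients should undergo the following", and adds: "Functional assessment will be performed just after undergoing the diagnostic coronary angiography".
- Section 5.3 lists "Obstructive coronary artery disease" among the exclusions, without saying when it is checked.

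Section 8 sets the significance level at 0.05 and names a chi-square or Fisher's exact test for comparing CMD between the groups.

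**The concern.** Read in sequence, these sections have patients consent and enrol before the angiogram. The angiogram is the natural point at which obstructive disease would be found, and CFR and IMR are measured straight after it. Some enrolled patients may therefore prove ineligible, and others may have no usable measurement. Section 4.5 has no inflation for this and no replacement rule, and it speaks of enrollees rather than patients with a primary outcome.

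The calculated 46.92 rounds up to 47, so rounding provides no reserve for losses. If recruitment stopped at 94 enrolled, the primary comparison would be made on fewer patients and the stated power of 0.9 would not be achieved. At stake is the chance of detecting a true difference, not the validity of the test.

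**Working it through.** **Inputs.** Prevalences 0.45 and 0.15, equal groups and power 0.9 come from 4.5; alpha 0.05 comes from section 8. Two assumptions are needed because the documents are silent: a two-sided test, and no continuity correction. Among the variants of the standard formula tried, this pair is the one that returns 94. The two-sided version with continuity correction gives 108; the one-sided versions give 78 without and 90 with the correction.

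**Step 1: the plan's figure.** With mean prevalence (0.45 + 0.15)/2 = 0.30,

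n = [1.96 × √(2 × 0.30 × 0.70) + 1.2816 × √(0.45 × 0.55 + 0.15 × 0.85)]² / 0.30²

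= [1.2702 + 0.7848]² / 0.09 = 46.92 per group.

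Rounded up, that is 47 per group and 94 in total, as stated.

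**Step 2: loss of one or a few patients.** Power is found by enumerating all outcomes of two binomials (0.45 and 0.15) and applying the uncorrected Pearson test at two-sided 0.05.

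| Group A / Group B | Exact power |
|---|---|
| 47 / 47 | 0.907 |
| 46 / 47 | 0.900 |
| 47 / 46 | 0.903 |
| 46 / 46 | 0.899 |

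Losing a single patient from either group leaves power at 0.9. Losing one from each puts it 0.001 below.

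**Step 3: larger losses, if 94 meant enrolled.** The loss rates are assumptions, applied equally to both groups. The last column repeats the enumeration at the source estimates of 50% and 10%.

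| Assumed loss | Measured per group | Power, 45% vs 15% | Power, 50% vs 10% |
|---|---|---|---|
| none | 47 | 0.907 | 0.995 |
| 5% | 45 | 0.898 | 0.994 |
| 10% | 42 | 0.872 | 0.990 |
| 20% | 38 | 0.840 | 0.983 |
| 30% | 33 | 0.788 | 0.968 |
| 40% | 28 | 0.716 | 0.936 |

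At the planning values the effect is negligible at 5%, visible from 10%, and substantial at 30% or more. At the source estimates power stays above 0.9 throughout.

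**Step 4: if 94 meant measured.** Power is then as stated, and the loss affects only how many patients are approached. Rounding 47/(1 − loss) up within each group: at 10%, 47/0.90 = 52.2, so 53 per group and 106 enrolled; at 20%, 47/0.80 = 58.75, so 59 per group and 118 enrolled.

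**Step 5: which reading fits the plan.** A patient found to have an exclusion criterion is not eligible, and by ordinary practice is recorded as a screening failure rather than counted in the target. Section 4.5 re-assesses the sample size from observed CMD prevalence, and CMD status exists only where CFR and IMR were obtained. Anyone carrying out that step has to count measured patients, would see a shortfall, and may continue recruitment.

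**The case for a change.** The strongest counter-argument is textual. Section 4.5 refers to completed enrolment and to enrollees, section 4.2 puts the angiogram after enrolment, and no section requires that a patient excluded at angiography be replaced. The re-assessment is driven by prevalence, not by a count of usable measurements, so a team following the words literally could stop at 94 consented patients. Imputation under section 8 would not help with patients who were never eligible.

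This stands as an observation about drafting: the section does not say what it counts. It does not establish a loss of power. That would need both the literal reading and a loss rate of roughly 10% or more, and the documents support no particular rate. Nor is it accurate to say that the plan has no margin at all. The 5-point shift of each prevalence is not an allowance for losses, but it is a deliberate reserve on the effect size and bears on how much power is really at risk.

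A related objection is that section 8 leaves the choice between chi-square and Fisher's exact test open, and that Fisher's test gives 0.865 at 47 per group. That matters only if Fisher's test is made the primary test, which the plan does not say. Under the usual rule of using it when an expected count is below 5, it would be triggered with probability about 6 in 10 million and power would stay at 0.907.

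**Conclusion.** The concern does not call for a change. The 94 patients are correct for the stated assumptions, taking a two-sided uncorrected chi-square test. The possible shortfall (power about 0.87 at 10% loss, 0.84 at 20%) depends on an assumed loss rate and on counting ineligible patients towards the target. Under the ordinary reading, in which the 94 are eligible patients with a primary measurement, power is 0.9 as stated. Under the other reading, the re-assessment in 4.5 gives the team an opportunity to notice the shortfall and continue recruitment, and the comparison of prevalence remains a valid test throughout. The gap is one of wording that analysts and site staff would fill sensibly.

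This conclusion rests on patients excluded at angiography being treated as screening failures. The documents do not state this, but nothing in them contradicts it beyond the loose use of the word enrollees.

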1. Data Management: All data collected will be entered into a secure, electronic database with backup systems in place. Double-entry methods and routine cross-checks will be implemented to minimize data-entry errors.
2. Descriptive Statistics: Basic statistics like mean, median, standard deviation, and interquartile ranges will be utilized to describe continuous variables. For categorical variables, frequencies and percentages will be used.
3. Comparative Analysis: To compare the incidence of CMD between Group A (COVID-19 with oxygen supplementation) and Group B (no history of COVID-19), a Chi-square test or Fisher's exact test will be employed for categorical variables, and the t-test or Mann-Whitney U test will be used for continuous variables, depending on the data distribution.
4. Correlation Analysis: Pearson's or Spearman's rank correlation will be used to assess the relationship between the duration of oxygen supplementation and the severity of CMD.
5. Significance Level : A p-value of less than 0.05 will be considered statistically significant for all tests.
6. Multiple Testing: Adjustments for multiple comparisons, if applicable, will be done using methods like the Bonferroni correction to prevent type I errors.
7. Missing Data: Any missing data will be addressed using suitable imputation methods. The extent and pattern of missing data will be analyzed, and if it's determined to be missing at random, multiple imputation methods may be used.
8. Subgroup Analysis: If sample size permits, further subgroup analyses might be performed to identify any trends or patterns within specific subsets of the population, such as based on age, gender, or other relevant factors.

9. Graphical Representation: Key results will be depicted using appropriate charts and graphs to aid in the visualization and interpretation of findings.

10. Software: All statistical analyses will be performed using a validated statistical software package like SPSS, R, or Stata.

11. Reporting: Results will be reported in accordance with relevant guidelines for observational studies, ensuring clarity, transparency, and reproducibility.

9. Regulatory issues

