10.1. Study reporting

Upon the completion of the study and subsequent data analysis, our findings will be compiled and prepared for dissemination in May 2024. The results will be structured following the typical format of an original research article, with sections including Introduction, Methods, Results, Discussion, and Conclusion. Preliminary findings will first be presented to the investigative team.

Feedback will be incorporated, and a finalized report will be prepared for submission to a peer-reviewed medical journal. Besides, we will seek opportunities to present our findings at relevant conferences and symposia, ensuring a wider reach among the medical and research community. All data will be archived as per regulatory guidelines, ensuring transparency and facilitating future reference or studies. Any post-publication queries or feedback will be addressed promptly by the research team.

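### Sample size is re-assessed from by-group CMD prevalence at 94 patients with no maximum N and no test adjusted for that look, so the 5% level is not guaranteed

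*Combined protocol and SAP*

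**What the plan says.** Section 4.5 sets the initial size: "For a study power of 0.9, we will require a total of 94 patients in the study", 47 per group, from assumed prevalences of 15% and 45%. It then declares an adaptive design. Once those patients are in, the sample size is to be "re-assessed to statistical power based on the observed prevalence of CMD within in each of the present cohort", and "the decision will be made to continue or halt enrollment depending on whether the necessary number of enrollees for statistical significance" on the primary endpoint has been reached.

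Section 8 (Statistics and data analysis) supplies the test. Item 3: "a Chi-square test or Fisher's exact test will be employed for categorical variables". Item 5: "A p-value of less than 0.05 will be considered statistically significant for all tests". Item 6: "Adjustments for multiple comparisons, if applicable, will be done using methods like the Bonferroni correction to prevent type I errors". None of these items mentions the look at 94 patients. Neither section gives a maximum N, a futility rule, an adjusted critical value or a combination test.

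On resources, Section 1.1 says "Anticipated recruitment is 6 months", Section 10.1 says "our findings will be compiled and prepared for dissemination in May 2024", and Section 9.7 says the study has no funding.

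**The concern.** The look is comparative: the observed difference between groups decides how many more patients are enrolled. When the final N depends on the interim difference and the ordinary test is then applied to all the data, that test no longer has its nominal level. How far it departs depends on three things the plan leaves open: how the continue-or-halt sentence is read, which test is used, and where enrolment must stop.

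The missing cap matters most. If the groups truly do not differ, the recomputed N is usually very large (median about 1,100 per group at a common prevalence of 15%). Two hospitals with six months' recruitment and no funding cannot enrol that many. In practice a stopping point would be chosen after the by-group results were known. This is the study's only primary test, and Section 4.4 says a significant association could change clinical decisions.

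**Working it through.** **Inputs.** From Section 4.5: prevalences 15% and 45%, power 0.90, 47 per group. From Section 8: level 0.05. Two-sided testing is an assumption; among the variants tried, only the two-sided pooled formula without continuity correction returns 94.

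**Reproducing 94.** n per group = [z(0.975)·√(2p̄(1−p̄)) + z(0.90)·√(p1(1−p1)+p2(1−p2))]² / (p1−p2)². With p̄ = 0.30: [1.960×√0.42 + 1.2816×√0.375]² / 0.09 = (1.270+0.785)² / 0.09 = 46.9, so 47 per group. The same formula needs 97 per group at 15 v 35, 161 at 15 v 30 and 392 at 20 v 30.

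**When the rule halts.** Over all possible outcomes at 47 per group, the smallest |Z1| with a recomputed N of 47 or fewer is 3.200, and the largest |Z1| with N above 47 is 3.167. So the literal rule halts only at |Z1| ≥ 3.20. With equal prevalences it continues in over 99.8% of trials.

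**Type I error.** Equal true prevalence of 10/15/30/45%. Literal reading: enrol to the N recomputed for 90% power, then test all data at 0.05. Exact enumeration was used, with simulation at 2,000. The caps are assumptions.

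| Chi-square design | Error | Change from fixed, in points, at 10/15/30/45% |
|---|---|---|
| Fixed, 47 per group | 4.9–5.9% | – |
| Literal, cap 94 per group | 5.1–5.4% | −0.5 / −0.2 / +0.2 / +0.3 |
| Literal, cap 188 | 6.0–6.4% | +0.1 / +0.6 / +1.0 / +1.6 |
| Literal, cap 2,000 (no effective cap) | about 7.2% | +1.2 / +1.7 / +2.1 / +2.3 |

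Other choices the wording allows:

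- **Halt if significant at 94, otherwise extend and retest (chi-square):** 8.0–9.2%, 9.3–10.0% and 10.2–11.1% at caps 94, 188 and 2,000.
- **Fisher, literal reading:** 3.0–3.8%, 4.0–5.1% and 5.5–6.2% at the same caps; fixed design 1.7–3.1%.
- **Chi-square, halting at 94 when the required N exceeds the cap:** 3.5–5.1% (cap 94) and 2.6–2.8% (cap 188). At cap 94 the power is 90.6/61.4/40.4% at 15 v 45, 15 v 35 and 15 v 30, no better than a fixed 47 per group (90.7/62.0/41.6%).

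**Estimation.** Under the literal reading with equal prevalences, an unadjusted 95% interval covers 94.4–94.8% (cap 94), 93.5–93.8% (cap 188) and 92.7–92.8% (no effective cap). At 15 v 45 with cap 94, 49% of trials are told to continue, and 40% of all trials are told to continue although already significant. The mean estimated difference is 31.5 points overall and 36.9 in trials that halt, against a true 30.

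**Level of the proposed test.** With equal weights, the bivariate normal probability of |Z1| ≥ 3.200 or |(Z1+Z2)/√2| > 1.963 is 0.0500. For 2.178 at both looks it is also 0.0500.

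**The case against.** The strongest reply is that 7.2% needs enrolment this study could not carry out. At sizes nearer to feasible the inflation is small: at cap 94 the error is within half a point of the fixed design, and at 10–15% prevalence it is slightly lower. Fisher, which Section 8 permits, stays below 4% there. Part of the excess over 5% belongs to the fixed chi-square test and not to the adaptation. On this view a named test and a stated cap would be enough, and a combination test is more than is needed.

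Much of this stands. The 7.2% is the outer value of the literal reading, not the expected error, and it also assumes 90% power in the re-assessment and that ties continue. Under the literal reading a cap of 94 with a named test does nearly all the work. The stop-on-significance reading is less natural, because the sentence turns on the number of enrollees and not on a p-value. The 40% figure concerns efficiency, and the fix below keeps that halt rule. The fix also leaves the upward bias in place.

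What does not stand is treating limited resources as a cap. They would force a stop at a point nobody has fixed in advance, after the group difference is known. Fisher is optional, and item 6 of Section 8 sets no level for this look. The combination test holds its level whatever cap the sponsor chooses.

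One criticism of that test is fair. Without a minimum extension, a few late patients carry as much weight as the first 94. At 15 v 45, 11% of trials add fewer than 10 per group; of these 7.1% fail the combination test, against 0.02% on the ordinary pooled test. The optional floor below addresses this.

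**Conclusion.** The concern holds. The re-assessment rule, taken with an unadjusted p<0.05, does not secure a 5% level, and the plan does not allow the level to be worked out. The literal reading with chi-square gives 5.1–5.4% at an assumed cap of 94 per group, 6.0–6.4% at 188 and about 7.2% with no effective cap. Stopping on significance gives 8.0–11.1%. Fisher with a modest cap, or halting when the required N is too large, would keep the error near or below 5%, but the plan commits to neither. These figures assume two-sided testing, re-assessment at 90% power by the formula that reproduces 94, and equal true prevalences of 10–45%. The point should be fixed before the look; the inflation is modest under most readings.

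**What to change.** Keep the by-group re-assessment and state the following in Section 4.5 before the look:

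1. One named primary test, for example uncorrected chi-square.
2. The halt rule made explicit: halt and claim a difference only if the N recomputed for 90% power is 47 per group or fewer; otherwise enrol to the recomputed N.
3. A maximum N set by the sponsor from recruitment capacity (94 per group is an example).
4. On continuing, a final test (Z1+Z2)/√2 against 1.963, with Z2 from patients enrolled after the look only. Simulated error is 4.8–5.1% at caps of 94, 141, 188 and 2,000.
5. The interval obtained by inverting the same test (simulated coverage 94.6–97.5%), with a statement that the point estimate keeps a small upward bias.

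A minimum of 71 per group on continuing is optional; it adds power and is not needed for validity.

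**Cost.** Protocol wording and a little power. Chi-square at cap 94:

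| | Power at 15 v 45 / 15 v 35 / 15 v 30 | Mean N per group |
|---|---|---|
| Plan, literal reading | 99.6 / 89.6 / 70.3% | 60 / 78 / 85 |
| Fix with floor of 71 | 99.4 / 88.7 / 69.1% | 64 / 80 / 87 |
| Fix without floor | 98.4 / 87.6 / 68.5% | as the plan |

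At cap 188 with the floor, power is 99.8/97.3/88.9% against 99.9/98.4/91.8% for the plan. The interval is wider (±3.20 SE) in trials that halt at 94. The mean estimate at 15 v 45 is 31.7 points, so the bias is not removed.

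**Alternatives.** If stopping for significance at 94 patients is wanted, use |Z| > 2.178 at both looks (error 5.0–5.3%; at cap 94, power 99.4/86.7/65.2% and mean N 54/69/78). The simpler option is to re-assess on pooled prevalence only, holding the 30-point difference, with a floor of 47 and a cap of 57 per group and one test at 0.05 (error 4.8–5.9%). That adds at most 2×(57−47) = 20 patients but does not protect power for smaller differences (62% at 15 v 35, 42% at 15 v 30).
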